A CCXOPRCT design initially randomly assigns hospice sites to two of three groups: 1) Group 1 participants will serve as the control and receive usual hospice care enhanced by hospice staff training in shared decision making, 2) Group 2 participants will receive enhanced usual care as well as participate in a private Facebook support group to increase their knowledge and provide social/emotional support, 3) Group 3 participants will receive enhanced usual care, participate in the Facebook support group, and participate in hospice team meetings with a shared decision making process. After 12 months the group goes through a 90 day (or less if all have completed the trial earlier) washout period so all participants can complete the study. The group then is assigned to a second arm of the study for another 12 months. Again following a washout period so all participants complete the trial and then re-assignment to their first study arm again. Each cluster will go through two arms of the intervention, although participants will only complete one arm. A schedule has been developed. We will use qualitative and quantitative methods in parallel and equal status to measure the efficacy of the intervention.

**Our overall hypothesis is that ACCESS will improve hospice cancer family caregiver knowledge and emotional state (via Facebook), thereby facilitating a shared decision making process, which will result in improved caregiver anxiety and knowledge and improved pain control for patients.**

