## **Study Procedures**

We propose an intervention to target education and emotional support to FCGs based on a structured process for SDM. ACCESS (Access for Cancer Caregivers to Education and Support for Shared decision- making) has three components; 1) Facebook groups to provide education and emotional

support to FCGs, 2) web-conferencing to involve FCGs in care plan meetings and, 3) a structured SDM process to guide team discussion. These components will facilitate SDM between the hospice staff and FCGs, lower FCG anxiety, and increase FCG knowledge regarding patient pain, resulting in less pain for cancer patients. A pragmatic cluster randomized controlled trial (PC-RCT) will randomly assign hospice sites to one of three groups: FCG participants at Group 1 sites receive only enhanced usual care (EUC), FCG participants at Group 2 sites receive EUC and participate in Facebook (FB) groups for informational and emotional support, FCG participants at Group 3 sites receive EUC, participate in Facebook groups and the interdisciplinary team meeting for SDM (FB/SDM). Usual hospice care will be enhanced through education on SDM for all staff.

This study will last five years. Participants will be in the study for up to 120 days, depending on the death or discharge of their patient. Team meetings are held every other week, Facebook groups will be visited at least two times per week. Data collection will be done on the following schedule: baseline (day one), day 14, day 30, day 60, day 90, and on or before day 120. Data collection may end earlier at 14-21 days after the death or termination of the patient from hospice services or if a study volunteer chooses to end their participation. A qualitative interview will be done on or around the same day that the last quantitative measures are gathered.

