## Randomization

We will use a cluster randomization design because:

1. Our aims contain individual level and organizational level outcomes. Study aim 3 can then be assessed at the organizational level as well as the individual level.
2. Given the large geographic distance covered by the six participating hospice sites, it is far more cost effective to focus our intervention costs at specific hospice sites rather than across all sites. This will allow us to assess the total impact of an agency wide intervention. In keeping with the pragmatic goal of our trial this is more reflective of how implementation would actually be done at a hospice site, as individuals would not be given random interventions in real life.
3. We will avoid the contamination between the intervention groups and the control group- an unavoidable consequence of having both groups in one hospice site. We believe contamination may have lowered our ability in the pilot study to detect the change in the primary outcome.
4. These sites provide us with a diverse sample. We will have rural and urban hospice programs, a greater number of under represented minorities, and a more diverse hospice staff.

We have chosen a cross over design to increase precision as each arm of the study may serve as its own control group, thus reducing the number of participants necessary to have adequate power. This has been the recommended design for small numbers of clusters that are not meeting recruitment goals.

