## Statistical Analysis

Statistical Assumptions: We will routinely test assumptions of linearity, independence and homoscedasticity by calculating and plotting residuals and Cook's distance for all models. Where data are missing, we will substitute the mode for categorical data and the median for continuous data, given that <0.5% of data were missing for any measure in our preliminary trial. If the proportion of missing data is higher, we will use multiple imputation. We use the final measure provided by caregiver before patient death in the analysis. Because individuals are randomly allocated and the sample size is relatively large, we expect that both known and unknown confounders will be distributed evenly among the three groups. Because randomization will be stratified by hospice, equivalent proportions from each hospice will be allocated to each group. However, we will test for an interaction effect between study group and hospice to assess whether the effect of the intervention differs between hospices. This will be tested by introducing a Study Group X Hospice interaction term into each of the regression models discussed below. We acknowledge that this study is not powered to detect small interaction effects. Additional confounders will only be introduced as covariates if we find evidence of imbalance between groups at baseline.

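### With two of three arms per hospice, the full fixed group-by-hospice interaction is not estimable, and the plan does not say which model supplies the arm effects

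*Combined protocol and SAP*

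**What the plan says.** The combined protocol and SAP describes the allocation in three ways.

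- **Abstract:** "A CCXOPRCT design initially randomly assigns hospice sites to two of three groups". After 12 months and a washout of up to 90 days, each site moves to a second arm. After another washout comes "re-assignment to their first study arm again". In summary, "Each cluster will go through two arms of the intervention, although participants will only complete one arm".
- **Study Procedures:** the trial "will randomly assign hospice sites to one of three groups".
- **Statistical Analysis:** allocation is described as made person by person, and "Because randomization will be stratified by hospice, equivalent proportions from each hospice will be allocated to each group".

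The number of clusters appears under Randomization: "Given the large geographic distance covered by the six participating hospice sites".

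The heterogeneity rule follows the third description directly: "This will be tested by introducing a Study Group X Hospice interaction term into each of the regression models discussed below". The only limitation conceded is low power for small interactions. The plan does not say whether the term is fixed or random. The equation under Statistical Analysis H1- H3 contains study group, baseline value and time since enrolment. It has no hospice term, no period term and no interaction.

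**The concern.** The interaction rule suits a trial in which each hospice supplies participants to all three groups. Under the Abstract, no hospice ever runs its third arm, because the third period repeats the first. The missing cells are empty by design, so recruiting more caregivers cannot fill them, and the caveat about power does not cover the problem.

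Two things are at stake. First, whether the effect differs between hospices can be answered for only part of the design, and a reader of the plan would not know this. Second, if the arm effects for H1 and H2 were taken from a model containing the fixed interaction, software that drops aliased columns without comment would print arm coefficients whose meaning depends on which hospice is the reference.

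**Working it through.** The plan gives no figure for this interaction, so there is nothing to reproduce. The check counts which parameters the design can estimate. The baseline and time covariates do not fill empty cells and can be set aside.

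1. **Inputs.** Six hospices (Randomization), three groups, and two arms per hospice with a return to the first (Abstract). The documents do not state which pair each hospice receives, or in what order.
2. **Cells.** 6 × 3 = 18 possible; 6 × 2 = 12 filled; 18 − 12 = 6 empty.
3. **Nominal size.** Interaction degrees of freedom: (3 − 1) × (6 − 1) = 10. Columns in the full model: 1 + 2 + 5 + 10 = 18.
4. **What is estimable.** Arm plus hospice has rank 1 + 2 + 5 = 8. With the interaction, rank cannot exceed the number of filled cells, 12. So 12 − 8 = 4 degrees of freedom are estimable and 10 − 4 = 6 are not. Put another way, the six within-hospice contrasts, less two arm parameters, leave 6 − 2 = 4. With two hospices per arm pair, 3 × (2 − 1) = 3 of these compare hospices sharing a pair, and the remaining one asks whether the three pairs agree with each other.
5. **Sensitivity to the unstated allocation.** There are 3^6 = 729 ways to give pairs to hospices. In 726 the ranks are 8 and 12, leaving 4 degrees of freedom. In the other 3 every hospice has the same pair, so one arm is never run; the ranks are 7 and 12, leaving 5.
6. **With period terms.** Assume all six ordered pairs on a common A-B-A calendar. Without the interaction, rank is 8 + 2 = 10. With it, rank is 12 + 1 = 13: within each hospice the second period coincides with the second arm, so only the third-versus-first period difference adds information. That leaves 13 − 10 = 3 degrees of freedom.
7. **Arm coefficients with the fixed interaction included.** With Group 1 as reference arm, each arm coefficient is a contrast within the reference hospice.

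| Reference hospice runs | Group 2 coefficient | Group 3 coefficient |
|---|---|---|
| 1 and 2 | estimable | not estimable |
| 1 and 3 | not estimable | estimable |
| 2 and 3 | not estimable | not estimable |
| any pair, period terms added | not estimable | not estimable |

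   A contrast averaged over all six hospices needs both arms at every hospice, so none is estimable when more than one pair is in use. Without the interaction, all arm contrasts are estimable: rank 8 of 8, or 10 of 10 with period.
8. **The other two descriptions.** One arm per hospice fills 6 cells; rank is 6 with or without the interaction, so 0 degrees of freedom remain. Fixed hospice and arm effects together then have rank 6 of 8, and no arm contrast is estimable. All arms at every hospice fills 18 cells; rank is 18 and all 10 degrees of freedom are available.

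**The case against.** Four points can be made for the plan.

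- **Something can be fitted.** A reader might infer that the interaction cannot be fitted at all. The documents do not support that. Four degrees of freedom (three with period) can be tested after aliased columns are dropped. The plan also specifies mixed models and does not call the term fixed; a random hospice-by-arm effect can be fitted despite empty cells, though weakly with six clusters. This stands: only the full fixed interaction is not estimable.
- **The arm effects need not be touched.** A reader might infer that following the rule destroys the H1 to H3 results. That is not shown either. The section introduces the term in order to test it, and the equation under Statistical Analysis H1- H3 leaves it out. On an ordinary reading it is a side test, whose result does not depend on reference coding. This stands in part: the plan asks for the term in every regression model and never says which model is reported, so the harm is conditional.
- **No hypothesis depends on this test, and low power is conceded.** True, and it limits the practical weight. But low power and non-estimability are different limitations, and only the first is disclosed.
- **The root is the unreconciled design.** Also true. The available degrees of freedom are 10, 4 or 0 depending on which of the three descriptions is followed. That is why reconciliation comes first in the fix.

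**Conclusion.** The concern holds for the full fixed interaction. Under the Abstract's crossover with six hospices, 4 of 10 interaction degrees of freedom are estimable, and this is true for 726 of the 729 possible pair allocations. The figure of 3 with period terms assumes all six ordered arm pairs on a common A-B-A calendar. The loss of one or both arm coefficients applies only if arm effects are read from a model with the fixed interaction. The plan leaves that open, and does not state that it will be done. The justification given for the rule, that "equivalent proportions from each hospice will be allocated to each group", is incompatible with a design in which no hospice runs all three arms. This should be corrected before analysis. It concerns a secondary check and the clarity of the reported model, and does not by itself invalidate the trial's comparisons.

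**What to change.** 1. Reconcile the Statistical Analysis section with the Abstract and Study Procedures so that one allocation is described throughout. If the crossover is the design in use, delete the statements that individuals were randomised and that allocation was stratified by hospice in equal proportions. State the arm pair and order for each hospice.
2. State that the H1 to H3 arm effects come from models with hospice and period terms and no fixed group-by-hospice interaction. This relies on the crossover; with one arm per hospice, fixed hospice effects would remove the arm contrasts.
3. Move heterogeneity to a separate secondary analysis, labelled descriptive. Use either a test of only the estimable interaction degrees of freedom, with their number stated, or a random hospice-by-arm effect, acknowledging how little six clusters can say about its variance.
4. If each hospice's own two-arm contrast is displayed with its 95% interval, state that it is not adjusted for period and is confounded with calendar time. On a common A-B-A calendar with period in the model, none of the six contrasts is estimable.

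The cost is SAP wording only. No further data are needed and participants are not affected.

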We will test whether randomization created balanced groups by comparing baseline measures and demographic characteristics, using chi-square or t-test analysis for categorical or continuous variables, respectively. Variables that differ significantly between groups will be included in regression models as potential confounders. To compare outcomes for Hypotheses 1-4 (H1-H4), we will use the last available measure post-baseline and prior to death or the end of the study. The last available measurement typically represents the FCG's measure at the last point prior to the patient's death. This is a last observation analysis. Carpenter and Kenward argue that, in such analyses, time to this event should be taken into account. We will therefore include time from study enrollment to the last observation as a covariate. We will report estimates with 95% confidence intervals. To draw inferences from our study to the likely benefit to an equivalent population where the intervention under trial is a model of service delivery, all analyses of outcomes will be by intention-to-treat. The intention-to-treat analysis, consistent with the objectives of a pragmatic trial, will minimize the influence of "informative missingness" of the data and preserve groups' comparability.

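### Every covariate beyond the baseline outcome and time since enrollment is chosen by baseline significance tests that ignore the six randomised hospices and take no account of prognostic value

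*Combined protocol and SAP*

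**What the plan says.** The Statistical Analysis section of the combined protocol and SAP sets the rule in two places. One limits adjustment to variables found to be imbalanced: "Additional confounders will only be introduced as covariates if we find evidence of imbalance between groups at baseline". The other says how imbalance is judged, "using chi-square or t-test analysis for categorical or continuous variables, respectively", and what follows: "Variables that differ significantly between groups will be included in regression models as potential confounders". The section gives no list of candidate variables and no significance threshold, and it does not say how a t-test is to serve three groups. Prognostic value is not a criterion.

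Two terms are outside the rule. The equation under Statistical Analysis H1-H3 always contains the baseline value of the outcome and time since enrollment, and the Statistical Analysis text separately commits to the time term.

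The expectation of balance is argued from individual allocation: "Because individuals are randomly allocated and the sample size is relatively large". The design sections say otherwise. The Randomization section describes a cluster design with "the six participating hospice sites", and the Abstract says: "Each cluster will go through two arms of the intervention, although participants will only complete one arm".

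**The concern.** A chi-square or t-test on caregivers treats each one as an independent draw. Caregivers of the same hospice share a catchment area, a referral pattern and a staff, and the arm is assigned to the hospice for a whole period. A variable that merely differs between hospices will therefore tend to differ between arms, and the unclustered test will call this significant more often than its nominal level.

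The rule also asks the wrong question. Whether a covariate is worth adjusting for depends mainly on how well it predicts the outcome. A significant baseline difference says nothing about that. A weak predictor that differs by arm goes in. A strong predictor of GAD-7 with a baseline p-value just above the threshold stays out, and the precision it would have given is lost. The stake is the efficiency of the primary comparison and the ability to write down the full covariate list before the data are seen.

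**Working it through.** The documents give no ICC, no power calculation, no baseline-test threshold and no figure for this rule, so there is no plan figure to reproduce. What follows is an illustration on stated assumptions.

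**Inputs**
- Six hospices (Randomization).
- Each hospice takes two of three arms and then returns to its first (Abstract), taken as A-B-A with each of the six ordered pairs of arms used once. This gives 6 × 3 = 18 hospice-periods, six per arm.
- 642 caregivers in total, the interview count under Qualitative Data. 642/18 = 35.7, taken as 36 per hospice-period. Equal cells are an assumption.
- Test level 0.05 and ICC 0.01, 0.02 and 0.05: assumptions.

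**Step 1: how far the naive variance is wrong.** In this layout any two arms differ in their hospice weights by ±1/6 for four hospices and ±2/6 for two. The sum of squares is (4 × 1 + 2 × 4)/36 = 12/36 = 1/3. If the correlation sits at hospice-period level instead, the sum is 12 × (1/36) = 1/3, so the split between the two does not matter. With unit total variance, the variance of an arm difference is ICC/3 + (1 − ICC) × 2/216. The naive test uses 2/216 = 1/108. The ratio is

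DE = 1 + (36 − 1) × ICC.

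**Step 2: flag rate.** A three-group test is close to a chi-square on 2 degrees of freedom, whose upper 5% point is 5.99. With no true imbalance, the chance of a flag is p = exp(−5.99/(2 × DE)).

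| ICC | DE | p, 36 per cell | p, 18 per cell (DE = 1 + 17 × ICC) |
|---|---|---|---|
| 0 | 1.00 | 5% | 5% |
| 0.01 | 1.35 | 11% | 8% |
| 0.02 | 1.70 | 17% | 11% |
| 0.05 | 2.75 | 34% | 20% |

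Simulations of the same layout gave 10-11%, 17% and 33-35% with 36 per cell, and about 8%, 10-11% and 20% with 18. A single pairwise t-test rejects in 9%, 13% and 24% at the same three ICCs with 36 per cell. The Study Procedures section still describes a parallel design with one arm per hospice. In that layout the pairwise rates would be 17%, 27% and 43%.

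**Step 3: precision lost.** Let R² be the share of outcome variance, after the baseline score, that one further covariate explains. Values of 5% and 20% are assumed. The rule adjusts only in flagged trials. The fraction of the covariate's contribution to the variance of the arm difference that remains is f = 1 − p × (1 − ln p). If the outcome residual has the same ICC as the covariate, the standard error under selection relative to always adjusting is √(1 + f × R²/(1 − R²)).

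| ICC | p | f | Excess SE, R² = 5% | Excess SE, R² = 20% |
|---|---|---|---|---|
| 0.01 | 0.109 | 0.65 | 1.7% | 7.8% |
| 0.02 | 0.172 | 0.53 | 1.4% | 6.4% |
| 0.05 | 0.336 | 0.30 | 0.8% | 3.6% |

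The range is about 1% to 8%.

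**Step 4: type I error.** Without clustering (214 per arm), the treatment test under the selection rule rejected a true null in 4.3% to 4.6% of runs. With clustering in the A-B-A layout (ten covariates, one of them predictive with R² = 10%, no hospice term in the model, 800 runs per setting):

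| ICC | Selection rule | Always adjusting for the predictor |
|---|---|---|
| 0.01 | 10.5% | 10.4% |
| 0.02 | 11.9% | 13.6% |
| 0.05 | 23.4% | 24.9% |

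Both columns are well above 5%, and selection is not the worse of the two by more than simulation error. The excess comes from leaving hospice out of the model.

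**The case against.** The strongest reply is that the most useful covariate is already safe. For GAD-7 the baseline score is the obvious strong predictor, and it is in every model whatever the tests show. This stands. A reader might infer that the whole adjustment set, or the primary model itself, is left to chance. The written equation does not support that; only further covariates are affected.

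A second reply is that selection uses baseline data and not outcomes, and that a flagged variable does differ between the arms in the sample, so adjusting for it need do no harm. This also stands. It is tempting to say that the confidence interval fails to reflect the selection step and so understates uncertainty. The checks showed no type I inflation from selection, with or without clustering.

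A third reply is that the figures depend on inputs the documents do not give. This is fair. The 642 is a count of interviews, and the Randomization section ties the cross-over to reducing the number of participants needed, so cells may be smaller; at 18 per cell the flag rates fall to 8%, 11% and 20%. The chance that at least one variable is flagged cannot usefully be stated, because neither the number of variables tested nor their correlation is known, and scales such as anxiety, depression and burden are likely to be correlated.

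The t-test remark is a minor point, since three pairwise tests are possible. What no reply answers is that the test is not calibrated for a trial of six clusters and that prognostic value has no part in the choice.

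**Conclusion.** The point holds for covariates beyond the baseline outcome and time since enrollment. The rule that selects them is miscalibrated for this design: about 11%, 17% and 34% of variables flagged instead of 5%, assuming ICCs of 0.01, 0.02 and 0.05, 36 caregivers per hospice-period, A-B-A order and a 0.05 threshold. Smaller cells give fewer flags. The cost is modest: a standard error about 1% to 8% larger than with always adjusting, for one covariate explaining an assumed 5% to 20% of the variance left after the baseline outcome. If little variance is left to explain, the cost is at the low end.

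The raised error rates in Step 4 should not be read as a result of this rule. They arise because the stated nesting is within participants only, which is a separate defect that a covariate list will not cure. This is a cheap improvement to the analysis plan, not a threat to the validity of the primary comparison.

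**What to change.** - Delete both statements in the Statistical Analysis section that make adjustment depend on baseline imbalance.
- Keep the baseline value of the outcome and time since enrollment as planned.
- Add to every H1-H3 model one short fixed list of prognostic covariates, named before outcome data by arm are examined. Draw it from items confirmed as collected under the list of family caregiver measures, for example caregiver demographics, patient diagnosis and baseline patient pain. For pain, name the instrument: the measures list gives the Edmonton scale, while the H1 and H2 text names the BPI.
- Present the baseline table by arm and by hospice, without p-values.
- Report adjustment for any unexpected imbalance as a labelled sensitivity analysis.

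This changes wording only. It costs a few degrees of freedom, and an unexpected imbalance is handled outside the primary model. How hospice and period enter the model should be settled at the same time, as its own item.
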